## 9.7.2 Endpoints

The adverse events of interest and the time periods when the subject is considered at risk after vaccination are presented in [Table 9.3-1](#).

## 9.7.3 Planned Analyses

Tabular summaries will be presented by treatment group. Categorical data will be summarized by the number and percentage of subjects in each category. Continuous variables will be summarized by descriptive statistics, including mean, standard deviation, median, minimum, and maximum. The age, gender, medical center, and prior year health care utilization level of the Q/LAIV and control groups will be summarized for descriptive purposes. Race information is not available in the Kaiser HMO databases.

Rates of events will be presented per 1,000 person-years. All statistical tests will be 2-sided and performed at the significance level of 0.05. Due to the exploratory nature of the study and the lack of formal hypothesis testing, multiple CIs will be constructed in the primary analysis without multiplicity adjustment. Due to the large number of unadjusted CIs to be evaluated, it is expected by chance alone that a number of CIs will not include one and suggest higher or lower event rates in the Q/LAIV group. Therefore, further statistical and medical assessments may be performed for events with observed increases that are statistically significant and/or medically important.

Incidence rates of adverse events of interest during periods at risk after Q/LAIV vaccination will be compared to incidence rates during reference periods later in the follow-up as presented in [Table 9.3-1](#) (within-cohort analysis) and to incidence rates in controls (matched unvaccinated subjects and matched IIV recipients).

Incidence rates will be reported as subjects with an event per 1,000 person-years. If a subject has more than one event in the analysis window, the subject will be counted only once for the analysis. Relative risks (RR) and corresponding 95% CIs will be constructed for each event for safety comparisons with control groups. Crude RR and adjusted hazard ratio (HR) and corresponding 95% CIs for each event will be derived:

- Crude RR and exact 95% CI will be calculated without adjustment of any covariate.
- Adjusted HR and corresponding 95% CI will be obtained using Cox proportional hazards model with calendar time data input adjusting for seasonal changes in

background rates and other confounders. This multivariable analysis is detailed in Section 9.7.4.

Statistical significance will be declared based on the multiple variable analysis using the Cox model. However, if the 95% CI of adjusted HR or p-value cannot be estimated, the exact method without adjustment of covariates will be used. A statistically significantly increased risk associated with Q/LAIV vaccination will be declared if the lower bound of the HR 95% CI is  $> 1.00$ . Likewise, a statistically significantly decreased risk associated with Q/LAIV vaccination will be declared if the upper bound of the HR 95% CI is  $< 1.00$ . Statistical significance will be evaluated before rounding. The corresponding p-values also will be provided. If any control group has zero events, the corresponding RR will not be estimable due to a zero value of the denominator. If the p-value is available, statistical significance will be declared according to the p-value at the 95% significance level.

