#### **9.5 Study Size**

Since there are no identified safety concerns with Q/LAIV, this post-marketing safety assessment is hypothesis generating and will include multiple statistical comparisons.

Enrollment of at least 10,000 children 2 through 8 years of age is planned. A sample size of 10,000 children will provide approximately 90% power to observe a statistically significant increase in relative risk (RR) of 1.5 for an event that occurs in 1 in 100 subjects in the comparison group. The study will also be able to rule out with 95% probability the occurrence of an event at a rate of 0.03% (1 in 3,333 subjects) assuming that incidence of the event follows a Poisson distribution. Enrollment is expected to be completed in the 2013-2014 influenza season but the study will be continued for additional seasons, if needed, until enrollment of 10,000 Q/LAIV recipients 2 through 8 years of age is completed to fulfill the postmarketing commitment to the FDA.

However, because the study is expanded to adolescents and adults up to 49 years of age, it is expected that a total of approximately 80,000 individuals will be enrolled (including approximately 10,000 to 30,000 individuals in each of the following 4 age groups: 2 to 4 years, 5 to 8 years, 9 to 17 years, and 18 to 49 years of age) during the 2013-2014 influenza season. Enrollment of 20,000 children per age group will provide approximately 90% power to observe a statistically significant increase in relative risk (RR) of 1.5 for an event that occurs in 1 in 200 subjects in the comparison group. A sample size of 20,000 will also be able to rule out with 95% probability the occurrence of an event with an incidence rate of 0.015% (1 in 6,666 subjects).

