#### 9.7.4 Multivariable Analysis

One of the primary challenges with performing safety assessment in this setting is that the background rates of many outcomes, such as respiratory events, change over time during the period of vaccination and follow-up. These changes in background rates are due to factors such as patterns in circulation of a variety of respiratory viruses and changes in exposure due to behavior influences such as the school year and holidays.

Controlling for seasonal changes in background rates that are dependent upon calendar time is important to minimize the potential seasonal bias and ensure that the effect of Q/LAIV on the rate of these events from a safety perspective, if any, can be accurately estimated.

The counting-process style of input for the Cox proportional hazards model can accomplish this by allowing the use of calendar time as the structure for defining the observation intervals ([Andersen and Gill, 1982](#)). Rows of observations for each subject will be generally structured as:

*pid, caldtst, caldtsp, event*

where *pid* is the subject identifier, *caldtst* is the calendar date of the beginning of the observation period, *caldtsp* is the calendar date of the end of the observation period, *event* is 1 if an event occurred at the end of the observation period, and 0 if an event did not occur, indicating censoring.

101,	11Oct2013,	22Nov2013,	0
102,	15Oct2013,	02Nov2013,	1

indicates that participant 101 was under observation from October 11 through November 22 and did not experience an event and was censored on November 22. Participant 102 was under observation from October 15 and experienced an event on November 02. Although not shown in this example, the values of main effects and covariates would also be included in each row.

This method controls for the effect of seasonal and other calendar time differences on background event rates because, when each component of the Cox partial likelihood is calculated at each event, the risk set includes only subjects who were under observation during the same calendar time period.

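### In the within-cohort comparisons with Days 43–84, the exact-test fallback declares significance with no calendar-time control, and nothing in the design replaces that control

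*Protocol*

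**What the plan says.** Section 9.7.3 sets the decision rule: "Statistical significance will be declared based on the multiple variable analysis using the Cox model". It then provides for failure of that model: when the adjusted interval or p-value is not estimable, "the exact method without adjustment of covariates will be used". The same section describes the exact analysis: "Crude RR and exact 95% CI will be calculated without adjustment of any covariate".

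Section 9.7.4 explains why the primary model runs on calendar time. Background rates, notably of respiratory events, shift during vaccination and follow-up, and "Controlling for seasonal changes in background rates that are dependent upon calendar time is important to minimize the potential seasonal bias". The control works through the Cox risk sets, which hold only people under observation on the same calendar date.

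Section 9.7.4.1 and Table 9.3-1 fix the within-cohort windows. Days 1–14, 15–42 and 1–42 are each compared with Days 43–84, and Days 0–3 with Days 7–9. Lower respiratory events, wheezing, any hospitalization and respiratory hospitalization all use the Day 43–84 reference. Section 9.7.1 adds analyses by four age groups and by three settings.

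**The concern.** Calendar time enters the analysis only through the Cox risk sets. When the fallback takes over, that control goes, and the protocol attaches no caveat or label to a result declared this way.

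The trigger is foreseeable. Section 9.7.4 builds intervals from a normal approximation. With no events in one of the two windows, the Cox coefficient runs to infinity and that interval cannot be formed. Section 9.7.3 itself anticipates groups with zero events.

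The direction matters in a safety study. If the background rises from the risk window to the reference window, the crude test too readily declares a decreased risk and needs too much evidence to declare an increase. Section 9.7.3 foresees further assessment for observed increases only, so a masked increase may get no second look.

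**Working it through.** **The plan's own figure.** The protocol gives no operating figure for the fallback. Its power statement in Section 9.5 is that "10,000 children will provide approximately 90% power to observe a statistically significant increase in relative risk (RR) of 1.5"; the comparison-group rate there is 1%. With 1:1 groups, the two-proportion normal approximation gives z = (0.005·√10,000 − 1.96·√(2·0.0125·0.9875)) / √(0.01·0.99 + 0.015·0.985) = (0.500 − 0.308)/0.157 = 1.22, or 88.9% power. The stated figure is reproduced, but it says nothing about sparse strata.

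**Inputs from the protocol.** "All statistical tests will be 2-sided and performed at the significance level of 0.05", so each tail is 0.025. Window lengths are 42, 14 and 42 days for Days 1–42, 1–14 and 43–84.

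**Assumptions.** Event counts are Poisson and the vaccine has no effect. R is the ratio of background rate in the reference window to that in the risk window; the documents give none, so a range is shown. A zero count in the risk window stands for a Cox interval that cannot be estimated.

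**Step 1: when the crude exact test declares a decrease with no risk-window events.** The crude null share of events in the reference window is q = 42/(risk days + 42). The test needs k events with q^k ≤ 0.025.
- Days 1–42: q = 0.5; 0.5^5 = 0.031, 0.5^6 = 0.016, so k = 6.
- Days 1–14: q = 42/56 = 0.75; 0.75^12 = 0.032, 0.75^13 = 0.024, so k = 13.

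**Step 2: how many events should be needed.** With background ratio R the true null share is 42R/(risk days + 42R).
- Days 1–42: 8 events at R = 1.5 (share 0.6; 0.6^8 = 0.017) and 10 at R = 2 (share 0.667; 0.667^10 = 0.017), not 6.
- Days 1–14: 19 at R = 1.5 (share 0.818; 0.818^19 = 0.022) and 24 at R = 2 (share 0.857; 0.857^24 = 0.025), not 13.
- An increase in Days 1–42 with an empty reference window: the crude test needs 6 events, where 5 would suffice at R = 1.5 (0.4^5 = 0.010) and 4 at R = 2 (0.333^4 = 0.012).

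**Step 3: chance that the fallback runs and declares a false decrease.** P = exp(−λ_risk) × P(Poisson(λ_ref) ≥ k), with λ_ref/λ_risk = R × 42/risk days, maximised over the total expected events.

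| R (assumed) | Days 1–42 | Days 1–14 |
|---|---|---|
| 1.0 | 0.4% | 0.8% |
| 1.5 | 1.5% | 3.0% |
| 2.0 | 3.2% | 6.2% |

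As an example, Days 1–42 at R = 2 peaks at λ_risk = 2.4 and λ_ref = 4.8: 0.091 × 0.348 = 3.2%. Days 1–14 at R = 1.5 peaks at λ_risk = 2.82 and λ_ref = 12.7: 0.059 × 0.504 = 3.0%. At 6 expected events in total, the chance of an empty reference window with a false increase (Days 1–42) falls from 0.4% at R = 1 to 0.03% at R = 2.

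**Step 4: whether a calendar-preserving fallback helps.** Assume vaccination from mid-September to end December with a mode in mid-October, and a threefold background peak near 30 December. In 4,000 simulations per setting, a zero cell with a false decrease occurred in 2.7% with the crude test and 0.1% with an exact test stratified by calendar day (Days 1–14, 20 expected events). For Days 1–42 with 10 expected events the figures were 0.8% and 0.2%. Over assumed peaks of two- to threefold, R was 1.22–1.35 for Days 1–42, 1.37–1.63 for Days 1–14, and only 1.05–1.09 for Days 0–3 versus 7–9.

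**The case against.** The strongest reply is that the fallback runs only where it can do little harm. With an empty risk window the exact test is conservative: for Days 1–42 the false-decrease probability stays under 2.5% until the background roughly doubles, and for Days 1–14 it passes 2.5% only near R = 1.5. This stands, and it sets the size of the point.

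Zero cells are also unlikely for the common outcomes in whole age groups. The annexed label reports wheezing in 2.1% of trivalent FluMist recipients aged 24–59 months through 42 days after the last dose, under a trial definition. In an age group of 10,000 that is 10,000 × 0.021 = 210 events, or about 70 in 14 days. The concern is therefore confined to sparse strata, such as respiratory hospitalization by age group or setting in a 14-day window.

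The study is described as hypothesis generating, and several rare diagnoses get case narratives whatever the test shows. That lowers the stakes, but Section 9.7.3 still makes formal declarations of increased and decreased risk.

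A reader might infer that every fallback result is seasonally biased. The documents do not support that. Unvaccinated controls share the index date and inactivated-vaccine controls the vaccination month (Section 9.1), Days 0–3 and 7–9 are nearly adjacent, and a flat season gives no bias. A reader might also infer that the error always flatters the vaccine; its direction depends on when vaccination falls relative to the peak. Nor does the protocol call calendar-time control essential or the exact test biased: it speaks of importance and of a potential bias. Finally, simulating the crude relative risk in the full cohort would not measure this problem, because with many events the Cox interval is estimable and the fallback never runs.

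**Conclusion.** The point holds for the within-cohort comparisons of Days 1–14, 15–42 and 1–42 with Days 43–84. There the stated rule lets a test without seasonal control decide significance, and nothing in the design restores the control.

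The effect is modest but real. It exceeds the nominal 2.5% tail at a background ratio of about 1.5 for Days 1–14 and about 2 for Days 1–42. These figures rest on assumed ratios, Poisson counts, and a zero risk cell as the trigger, and are maxima over the expected event count. If the Cox model failed with events in both windows, the crude test would do worse: at R = 1.5 for Days 1–42, false decreases would be 9.7% with 20 expected events and 24.9% with 50. The protocol gives no indication of how often that would happen.

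**What to change.** For the Day 43–84 within-cohort comparisons, amend the fallback sentence in Section 9.7.3 to name one calendar-preserving method: either a Firth-penalised Cox model on the same calendar-time rows with a profile-likelihood interval, or an exact conditional test stratified by calendar week, splitting each week's events by person-days in the risk and reference windows. Report the crude exact relative risk as descriptive, labelled as unadjusted for season. The fallback for matched-control comparisons and for Days 0–3 versus 7–9 can stay.

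The drafting cost is a sentence or two. The statistical cost is wider intervals, because calendar periods with only risk time or only reference time carry no information. Assuming a flat season and vaccination spread evenly over 90 days, stratifying by day loses about 24% of events for Days 1–42 and 51% for Days 1–14. Taking information as Σ rf/(r+f) over days, with r and f the risk and reference person-days, log-scale intervals widen by about 25% and 43%. The primary calendar-time Cox model already accepts the same loss, so this is no reason to give it up only where the data are sparse.

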#### 9.7.4 Multivariable Analysis

One of the primary challenges with performing safety assessment in this setting is that the background rates of many outcomes, such as respiratory events, change over time during the period of vaccination and follow-up. These changes in background rates are due to factors such as patterns in circulation of a variety of respiratory viruses and changes in exposure due to behavior influences such as the school year and holidays.

Controlling for seasonal changes in background rates that are dependent upon calendar time is important to minimize the potential seasonal bias and ensure that the effect of Q/LAIV on the rate of these events from a safety perspective, if any, can be accurately estimated.

The counting-process style of input for the Cox proportional hazards model can accomplish this by allowing the use of calendar time as the structure for defining the observation intervals ([Andersen and Gill, 1982](#)). Rows of observations for each subject will be generally structured as:

*pid, caldtst, caldtsp, event*

where *pid* is the subject identifier, *caldtst* is the calendar date of the beginning of the observation period, *caldtsp* is the calendar date of the end of the observation period, *event* is 1 if an event occurred at the end of the observation period, and 0 if an event did not occur, indicating censoring.

101,	11Oct2013,	22Nov2013,	0
102,	15Oct2013,	02Nov2013,	1

indicates that participant 101 was under observation from October 11 through November 22 and did not experience an event and was censored on November 22. Participant 102 was under observation from October 15 and experienced an event on November 02. Although not shown in this example, the values of main effects and covariates would also be included in each row.

This method controls for the effect of seasonal and other calendar time differences on background event rates because, when each component of the Cox partial likelihood is calculated at each event, the risk set includes only subjects who were under observation during the same calendar time period.

This style of input facilitates the use of calendar time and time-dependent covariates as the time structure of the model. The RR for the main effect (or a covariate) will be estimated by  $e^{\beta}$ , where  $\beta$  is the regression coefficient for the specific effect or covariate of interest. Ninety-five percent CIs for the RR will be calculated using a normal approximation, with the variance derived from the appropriate diagonal element of the estimated covariance matrix.

#### **9.7.4.1 Within-cohort Analyses**

Within-cohort analyses will be conducted among Q/LAIV recipients to see if the incidence of safety outcomes is higher within an immediate post-vaccination “risk” period (eg, 0 to 3, 1 to 14, 15 to 42, and 1 to 42 days post vaccination) compared to later “reference” periods, ie, 7 to 9 days post vaccination for the risk period of 0 to 3 days, 43 to 84 days post vaccination for the risk periods of 1 to 14, 15 to 42, and 1 to 42 days.

This will be accomplished in the Cox models by evaluating the main effect of “period,” defined as a time-dependent variable using the counting-process style of data input. Covariates, stratification factors, and the calendar time structure will be incorporated to control for the effects of age, gender, level of health care utilization, and seasonal difference in background event rates. The main effect variable of “period” will compare post-vaccination “risk” periods to “reference” periods occurring after the risk period.

For each study subject, the beginning of each reference period will follow the end of the risk period.

For example:

*riskperiod03*: 1 = risk (Days 0 through 3)

0 = reference (Days 7 through 9)

*riskperiod142*: 1 = risk (Days 1 through 42)

0 = reference (Days 43 through 84)

If specific results from the primary analyses identify a statistically significant increased risk associated with Q/LAIV administration, additional models with main effects structured to compare the “risk” periods to “reference” periods occurring prior to vaccination may be constructed. To reduce the potential bias associated with the “healthy patient effect,” the reference period prior to vaccination would exclude the week immediately prior to vaccination.

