### POPULATION

Individuals vaccinated with Q/LAIV and controls will be identified for inclusion in this study via the Kaiser Immunization Tracking System (KITS) database. Immunizations of KP members are recorded in this database as part of routine care. Because each recipient has a unique medical record number assigned once enrolled in the KP Health Care Plan and because administration records of all vaccinees are entered in the KITS database, the study population can be assembled from the KITS system on an ongoing basis. The lot number of administered vaccine is entered in the KITS immunization database for each vaccinee.

Subjects must meet *all* of the following criteria:

- 1) Age 2 through 49 years (prior to 50th birthday) at the time of vaccination (or index date for unvaccinated controls)
- 2) Membership in the KP Health Care Plan for at least 12 months prior to vaccination/index date
- 3) Continuous enrollment in the KP Health Care Plan through 6 months following vaccination/index date.

There are no exclusion criteria. Subjects with any high-risk underlying medical condition as defined by ICD-9-CM codes or successor (Annex 3) will be analyzed separately.

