- 1) Inactivated influenza vaccine recipient controls who received the current IIV formulation (trivalent or quadrivalent) but not Q/LAIV for the season at a Kaiser health maintenance organization (HMO) during the same month that the reference Q/LAIV recipient was vaccinated will be identified and matched based on age (year) and medical center relative to concurrent reference Q/LAIV recipients, using frequency matching. For children 2 to 4 years of age, matching by age will be based on calendar quarter of birth rather than year. Factors such as gender and prior health care utilization level will be included as covariates in the proposed Cox proportional hazards model.
- 2) Unvaccinated controls who did not receive any influenza vaccine for the season will be identified and matched based on age (year) and medical center relative to concurrent reference Q/LAIV recipients using frequency matching. For children 2 to 4 years of age, matching by age will be based on calendar quarter of birth rather than year. Factors such as gender and prior health care utilization level will be included as covariates in the proposed Cox proportional hazards model. Unvaccinated controls will be followed from the date of vaccination of the reference Q/LAIV recipient (the index date).

Health care utilization levels will be defined as “high” ( $\geq 2$  visits to a Kaiser HMO within the 6 months prior to the date of vaccination of the reference Q/LAIV vaccinee) or “low” ( $\leq 1$  visit).

The study is expected to begin in the fall of 2013 following the launch of Q/LAIV and to be completed in a single influenza season. However, if fewer than 10,000 Q/LAIV recipients 2 through 8 years of age are identified following the 2013-2014 influenza season, the study will be continued for additional seasons until enrollment of 10,000 Q/LAIV recipients is completed. A detailed description of safety follow-up is described in Section 11. Data will be collected on subjects for 180 days following vaccination (or the index date for unvaccinated controls).

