### 9.2.2 Inclusion Criteria

Subjects must meet *all* of the following criteria:

- 1) Age 2 through 49 years (prior to 50th birthday) at the time of vaccination (or index date for unvaccinated controls)
- 2) Membership in the KP Health Care Plan for at least 12 months prior to vaccination/index date
- 3) Continuous enrollment in the KP Health Care Plan through 6 months following vaccination/index date.

There are no exclusion criteria. Subjects with any high-risk underlying medical condition as defined by ICD-9-CM codes or successor ([Annex 3](#)) will be analyzed separately.

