## **9.9 Limitations of the Research Methods**

This study presents several limitations that are associated with its general design, the data sources, and the study size and power.

Because this study is observational and the decision to vaccinate against influenza is not controlled, the measure of the association between incidence rate of adverse events and vaccination status is exposed to several potential biases, in particular, to an indication bias: subjects who received Q/LAIV may differ from subjects vaccinated with IIV or unvaccinated subjects and present a different risk of adverse events. In order to control for this bias, incidence rates of adverse events of interest during periods at risk after Q/LAIV vaccination will be compared to incidence rates during reference periods later in the follow-up (within-cohort analysis). Additionally, subjects in the two control groups, ie, unvaccinated controls and IIV recipient controls, will be matched with subjects in the Q/LAIV group by age and medical center. Unvaccinated controls will be followed from the date of vaccination of the reference Q/LAIV recipient (ie, the index date). Other potential confounders such as gender and prior health care utilization level will be included as covariates in the proposed Cox proportional hazards model. A complementary analysis will be conducted after exclusion of subjects with high-risk underlying medical conditions.

All the study data are extracted from NCKP clinical and institutional databases; study data can be tracked via an automated audit trail. Databases are thoroughly validated within the Kaiser Permanente system, and are utilized for patient care and management, operational quality assurance, billing, and as a secondary use for research efforts. However, only medically attended events are documented and can be identified according to an ICD-9 diagnosis code, and only a limited number of critical adverse events can be validated against medical chart specifically for this study. Of note, the same limitations apply to adverse events documented during different periods of time, ie, at-risk periods as well as reference periods, and for different subjects, ie, Q/LAIV recipients and matched controls. Therefore, limitations regarding the validity of the data may impact the crude incidence rate estimates of adverse events but should not generate systematic biases of the association between incidence rates and vaccination status.

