**7.3 Concomitant Administration with Inactivated Vaccines**

The safety and immunogenicity of FluMist Quadrivalent when administered concomitantly with inactivated vaccines have not been determined. Studies of FluMist and FluMist Quadrivalent excluded subjects who received any inactivated or subunit vaccine within two weeks of enrollment.

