**7.4 Concomitant Administration with Other Live Vaccines**

Concomitant administration of FluMist Quadrivalent with Measles, Mumps, and Rubella Virus Vaccine Live (MMR, manufactured by Merck & Co., Inc.) or the Varicella Virus Vaccine Live (manufactured by Merck & Co., Inc.) has not been studied. Concomitant administration of FluMist with MMR and the varicella vaccine was studied in children 12 through 15 months of age [see *Clinical Studies* (14.5)]. Concomitant administration of FluMist with the MMR and the varicella vaccine in children older than 15 months of age has not been studied.

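### Other vaccines given on the same day as Q/LAIV are not handled anywhere in the design, so the Day 0–3 hazard ratios cannot separate their acute reactions from those of Q/LAIV

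*Protocol*

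**What the plan says.** Exposure is receipt of Q/LAIV in routine care. Section 9.2.2 states "There are no exclusion criteria". In Section 9.1 both control groups are "matched based on age (year) and medical center relative to concurrent reference Q/LAIV recipients", and IIV controls must also have been vaccinated in the same month. Unvaccinated controls are defined only by having had no influenza vaccine that season, and they take the reference recipient's vaccination date as their index date.

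On adjustment, Section 9.1 says: "Factors such as gender and prior health care utilization level will be included as covariates in the proposed Cox proportional hazards model". Sections 9.7.4.1 and 9.7.4.2 say the models will "control for the effects of age, gender, level of health care utilization, and seasonal difference in background event rates". Section 9.9 says: "Other potential confounders such as gender and prior health care utilization level will be included as covariates". None of these sections mentions other vaccines given on the same day.

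Table 9.3-1 sets Days 0–3 as the risk period for hypersensitivity and seizures/convulsions, with Days 7–9 as reference. Section 9.7.3 declares an increased risk associated with Q/LAIV when the lower 95% limit of the hazard ratio exceeds 1.00.

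Only the annexed package insert raises co-administration. Its Section 7.3 says: "The safety and immunogenicity of FluMist Quadrivalent when administered concomitantly with inactivated vaccines have not been determined". It adds that earlier FluMist and FluMist Quadrivalent studies excluded people given an inactivated or subunit vaccine within two weeks of enrollment. Its Section 7.4 says: "Concomitant administration of FluMist with the MMR and the varicella vaccine in children older than 15 months of age has not been studied". On the data source, the Abstract says of KITS: "Immunizations of KP members are recorded in this database as part of routine care".

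**The concern.** Sections 9.1 and 9.9 rely on the within-cohort comparison to deal with differences between vaccinated and other people. That comparison removes characteristics that stay constant within a person. It does not remove a second exposure that begins on the same Day 0. If another vaccine causes an acute reaction, the event falls in Days 0–3, is largely absent from Days 7–9, and loads onto the period effect. The optional follow-up model in Section 9.7.4.1, with a reference period before vaccination, has the same blind spot.

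The unvaccinated comparison shares the problem, because those controls need no vaccination visit on their index date. The IIV controls do have such a visit, so the bias there depends on how the two groups' co-vaccination rates differ.

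At stake is what a Day 0–3 result means. Under the Section 9.7.3 rule, a hazard ratio raised by another vaccine would be reported as a Q/LAIV risk.

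**Working it through.** **The plan's own figure.** Section 9.5 gives about 90% power for RR 1.5 with 10,000 children and an event rate of 1 in 100. Take 1:1 groups and a two-sided 0.05 test:

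- Standard error under the null = √(2 × 0.0125 × 0.9875 / 10,000) = 0.001571; under the alternative it is also 0.001571.
- z = (0.005 − 1.96 × 0.001571) / 0.001571 = 1.22, so power is 0.889.
- The 20,000-subject scenario at 1 in 200 gives 0.887.

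Both agree with the plan and are not disputed. RR 1.5 serves below only as a benchmark.

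**Is the factor handled anywhere?**

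| Place | What is handled | Other same-day vaccines |
|---|---|---|
| 9.2.2 eligibility | age, plan membership | not excluded |
| 9.1 matching | age, medical center, month (IIV only) | not matched |
| 9.7.4.1 and 9.7.4.2 models | age, gender, utilization, calendar time | not named |
| 9.9 limitations | indication bias, data validity, size | not named |

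**Size in the within-cohort and unvaccinated comparisons.** Let c be the share of Q/LAIV recipients given another vaccine that day, and r that vaccine's relative risk in Days 0–3. Both are assumptions, since the documents give neither. Assume also that Q/LAIV has no effect, that the reaction does not extend into Days 7–9, and that unvaccinated controls receive nothing on the index date. Then:

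apparent RR = (1 − c) × 1 + c × r = 1 + c(r − 1)

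| c | r | apparent RR |
|---|---|---|
| 10% | 2 | 1 + 0.10 × 1 = 1.10 |
| 20% | 2 | 1 + 0.20 × 1 = 1.20 |
| 20% | 3 | 1 + 0.20 × 2 = 1.40 |
| 30% | 3 | 1 + 0.30 × 2 = 1.60 |

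The last value exceeds the benchmark of 1.5. A delayed reaction falling in Days 7–9 would instead pull the within-cohort estimate down.

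**Size against IIV.** With shares cQ (Q/LAIV) and cI (IIV), and effects that multiply:

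apparent RR = true RR × [1 + cQ(r − 1)] / [1 + cI(r − 1)]

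Take a true RR of 1.5 and r = 3:

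- cQ = 10%, cI = 30%: 1.5 × 1.20 / 1.60 = 1.125.
- cQ = 30%, cI = 10%: 1.5 × 1.60 / 1.20 = 2.00.
- Equal shares: 1.5, no bias. If excess risks add instead of multiplying, equal shares of 20% give (1.5 + 0.4) / (1 + 0.4) = 1.36.

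**Effect of restriction.** Limiting the comparison to subjects with no other vaccine that day sets c to zero in every group, and the bias term becomes 1.

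**The case against.** The strongest reply is that this is an omission which a SAP could fill. The covariate wording in Sections 9.1 and 9.9 is open-ended, and restricted reruns are usual SAP content. The protocol calls the study hypothesis generating, says further assessments may follow a significant increase, and requires a narrative for every hypersensitivity and seizure case. It also accepts that residual differences between Q/LAIV and IIV recipients may bias the rates. Studying the vaccine as it is used, co-vaccination included, is a legitimate choice.

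Part of this stands. The narratives allow case-level review, and a signal would lead to follow-up, not to a settled causal conclusion. But narratives do not correct a hazard ratio or reveal a masked risk, and the further assessments are optional and name no co-vaccination check. Nor would one more fixed covariate repair the within-cohort contrast: a flag that is constant for a subject cannot absorb an effect confined to that subject's risk period.

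Four stronger readings are tempting, and the documents do not support them:

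- *The IIV comparison hides harm.* The direction depends on which group is co-vaccinated more, and the documents do not say. If Q/LAIV has no effect, a ratio below 1 would be spurious protection, not hidden harm.
- *The Day 1–42 outcomes are equally affected.* The argument concerns acute reactions. Nothing in the documents shows that a short-lived reaction matters over 42 days.
- *The documents say nothing reassuring about co-administration.* Section 6.1 of the insert reports that adverse reactions with MMR and varicella vaccines in Study AV018 resembled those in other FluMist trials. That study enrolled children of 12 to 15 months, below this study's age range, so it does not settle the matter.
- *The study cannot answer its question.* The bias could be trivial if co-vaccination is rare or the other vaccines cause few such events.

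**Conclusion.** The point holds for the Day 0–3 outcomes. As written, the within-cohort and unvaccinated comparisons credit Q/LAIV with acute reactions to any vaccine given alongside it, and the IIV comparison can be biased up or down. This goes beyond missing detail: carrying out the stated models and decision rule as written can produce the misattribution.

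The size is unknown. The range of 1.10 to 1.60 illustrates the mechanism under assumed c and r, and does not estimate the bias in this study. I attach no false-positive probability to it, because the protocol's 1-in-100 rate is a generic power scenario and not a Day 0–3 event rate. The change is worth making because it is cheap and the tabulation would itself show whether the problem is material. It is not a flaw that invalidates the design.

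**What to change.** Amend Sections 9.7.4.1, 9.7.4.2 and 9.9 as follows:

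1. Extract from KITS a flag for any other vaccine given on the vaccination or index date, and tabulate it by group.
2. For Days 0–3, add the flag as a covariate in the Q/LAIV versus IIV model.
3. For Days 0–3, prespecify a sensitivity analysis that repeats the within-cohort and both matched comparisons in subjects with no other vaccine that day.
4. Report the restricted hazard ratio and 95% interval beside the main result, and judge consistency by the estimates. Do not make a Q/LAIV signal depend on significance persisting in the restricted set: with fewer events a real signal could lose significance through power alone, and a reaction specific to co-administration would be dismissed.
5. State the limitation in Section 9.9.

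The cost is one extra field from a database already in use, one covariate and one rerun. No new data collection is needed and care does not change. The restricted set will have fewer events and wider intervals, which matters most for rare outcomes.
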